2.3.2 Demographic and other baseline characteristics

Demographics (date of birth (Age), sex, height and weight, BMI, predominant race and ethnicity), ECOG Performance Status by grade will be summarized descriptively using FAS and listed, unless stated otherwise.

Details on MDS diagnosis (initial diagnosis, WHO classification, current disease status (de novo or secondary) and cytogenetic abnormalities) will be tabulated and time since diagnosis will be summarized by each risk classification.

Disease history (MDS), including date of diagnosis, confirmation of MDS diagnosis, IPSS-R risk classification for MDS subjects at time of screening, prior antineoplastic therapies.

Medical history

Medical history (e.g., important medical, surgical, and allergic conditions from the subject's medical history which could have an impact on the subject's evaluation) / current medical conditions (e.g., all relevant current medical conditions which are present at the time of signing informed consent). Ongoing medical conditions, symptoms and diseases which are recorded on the Medical History eCRF must include the toxicity grade when applicable.

Relevant medical histories and current medical conditions at baseline will be summarized by system organ class and preferred term. Medical history and current medical conditions will be coded using the Medical Dictionary for Regulatory Activities (MedDRA) terminology. The MedDRA version used for reporting will be specified in the CSR and as a footnote in the applicable outputs.

2.4 Treatments (study treatment, rescue medication, concomitant therapies, compliance)

2.4.1 Study treatment / compliance

The duration of exposure will be summarized for study treatment and for each study drug (MBG453 (sabatolimab) and HMA (separately and combined together for all HMA)). The dose intensity (computed as the ratio of actual cumulative dose received and actual duration of exposure) and the relative dose intensity (computed as the ratio of dose intensity and planned dose intensity) will be summarized for each study drug MBG453 and for HMA individual component by descriptive statistics.

For MBG453, the actual cumulative dose in mg is the sum of “dose administered” from the eCRF of all cycles during the exposure of MBG453. For HMA (azacitidine, decitabine and INQOVI (oral decitabine), the actual dose in mg/m² in each cycle is the “dose administered” in mg during that cycle divided by the body surface area (BSA) at the beginning of the cycle using the weight measured before the infusion at that cycle. The actual cumulative dose in mg/m² is then the sum of all cycles. The following formula is used for BSA:

$$\text{BSA (m}^2\text{)} = \sqrt{\text{Weight (kg)} * \text{Height at screening (cm)} / 3600} \text{ (Mosteller formula)}$$

The duration considered for the derivation of the dose intensity and the relative dose intensity will be derived from the start date of study drug to the end of the last cycle initiated irrespective of date of death, last contact date for withdraw consent and cut-off date: the last exposure to study treatment (combination) will be the planned end date (Day 28) of the last cycle initiated with MBG453 and/or HMA, whichever is the latest. Details are provided in section [5. Appendix](#).

The relative dose intensity is then comparing the actual dose intensity during subject's exposure with the protocol planned dose of 800 mg Q4W for MBG453 and 20 mg/m² for decitabine, 75 mg/m² for azacitidine and Decitabine Oral (INQOVI) (100mg cedazuridine / 35mg decitabine), e.g. if a subjects received 300 mg Q2W on average throughout the study, the relative dose intensity for this subject is 0.75.

Dose reductions, interruptions or permanent discontinuations

The number and percentage of subjects with any dose changes of MBG453 (incl. interruptions, or permanent discontinuations) and the reasons will be presented.

The number and percentage of subjects with any dose changes (incl. reductions, interruptions, or permanent discontinuations) and the reasons (e.g. AE, dosing error, dispensing error, and physician decision) will be taken from the ‘Study Treatment eCRF’ and summarized by HMA. The total duration of interruptions by subject will be summarized for the study population by time intervals, e.g. < 1 week, ≥ 1- < 2 weeks, ≥ 2- < 3 week etc. (these time intervals may be adjusted depending on the observed data).

2.4.2 Prior, concomitant and post therapies

Prior and concomitant medications

Concomitant medications and significant non-drug therapies prior to and after the start of the study treatment will be summarized according to the Anatomical Therapeutic Chemical (ATC) classification system.

Each medication has the start and end dates recorded on the eCRF. Prior medications are defined as those medications which were taken and stopped prior to first dose of study treatment. Concomitant medications are defined as any medication given at least once between the day of first dose of study treatment and the last day of study visit, including those which were started pre-baseline and continued into the treatment period.

All concomitant medications will be listed and summarized in alphabetic order according to Anatomical Therapeutic Chemical (ATC) classification system and PT. All summaries will be performed on the Safety set.

Prior anti-neoplastic therapies

Prior anti-neoplastic medications, radiotherapy or surgery will be summarized using the FAS. Medications will be summarized by ATC class and preferred term. Radiotherapies and surgeries will be summarized by system organ class and preferred term.

Anti-neoplastic medications will be coded using the WHO Drug Dictionary (WHO-DD); antineoplastic surgery will be coded using MedDRA.

Transfusions

All transfusions of blood products (incl. those not related to MDS) prior and after start of study treatment will be listed. Only MDS related transfusions of platelet and red blood cells will be summarized using the FAS. For that, the number of transfusion episodes will be normalized by time (e.g. fixed 8-weekly interval) prior to and on-treatment.

Post treatment anti-neoplastic therapies and HSCT

Anti-neoplastic medications after discontinuation of study treatment during follow-up within the study will be summarized by ATC class and preferred term. HSCTs will be also summarized with the source, the type of transplant and the allogenic donor type if applicable. Both analyses will be using the FAS.

2.5 Analysis of the primary objective

The primary objective of this study is to assess the safety profile of MBG453(sabatolimab) 800mg (every 4 weeks) given in combination with HMAs (IV/SC/Oral).

2.5.1 Primary endpoint

The primary variables for this study are incidence of AEs and SAEs, and changes in laboratory values and vital signs.

Note: As primary objective of the study is safety objective and detailed analysis will be described in section 2.8, safety analysis

2.5.2 Statistical hypothesis, model, and method of analysis

No formal hypothesis testing is planned for this study.

2.5.3 Handling of missing values/censoring/discontinuations

Missing data for safety and efficacy endpoints will not be imputed.

2.5.4 Supportive analyses

Subgroup analysis may be performed as described in section 2.2.1.

2.6 Analysis of the key secondary objective

There is no key secondary objectives for this study and hence this section is not applicable.

2.7 Analysis of secondary efficacy objective(s)

For all secondary efficacy analyses, the Full Analysis Set (FAS) will be used for all subjects, unless stated otherwise.

2.7.1 Secondary endpoints

Following are the secondary endpoints to be considered for analysis by 12 months post LPFT and for complete available data for the study. Additionally for OS analysis by 24 months post LPFT will also be analyzed.

A listing of all responses assessments by subject will be provided including BOR, PFS time, PFS event (yes/no), OS time, death date and duration of CR. Bone marrow blasts percentage will also be listed. In addition, for some selected laboratory parameters and for bone marrow blasts percentage, trends over time will be displayed via boxplots and corresponding tables displaying the summary statistics for these selected timepoints to be produced.

2.7.1.1 Complete remission rate:

Complete remission rate will be assessed according to International Working Group (IWG) for MDS (2006) with MBG453 (sabatolimab) in combination with HMAs (IV/SC/Oral) in subject with intermediate, high, or very high risk MDS.

Proportion of subjects achieving CR will be presented together with an exact 95% confidence interval.

A sensitivity analysis may be performed for CR by considering IWG-MDS & modified IWG-MDS of Peripheral blood.

If any subject who achieved CR and discontinued/lost to follow-up within 12 months will be considered as Responder.

If any subject who achieved CR and undergone to Bone Marrow Transplantation (BMT) within 12 months will be considered as Responder.

Subjects who discontinue early before achieving response will be considered as non-responders. Similarly subjects with transplant or subjects with progression before achieving response will be considered as non-responders. As appropriate, additional sensitivity analyses will be performed excluding discontinued subjects, transplant subjects and subjects with progression before documentation of CR.

Response assessment rules

Response assessment will be performed by the investigator according to the assessment schedule depicted in protocol Table 8-1 based on available bone marrow assessment and peripheral blood every 3 cycles for core phase during the first 07 cycles and every 6 cycles for extension phase and all transfusions records as detailed in [Table 2-6](#) using the modified version of the published response criteria IWG for MDS. Moreover, response assessments can be performed at any time if clinically indicated, e.g. for confirmation of response but also for any suspicion of progression/relapse. These assessments are recorded as an unscheduled visit in the eCRFs and will be considered for the overall determination of response and progression/relapse with the respective assessment date.

The investigator does not determine best overall response, he/she is assessing only the response based on the given bone marrow and peripheral blood data, the history of transfusions and myeloid growth factor received within the last 2 weeks.

The best overall response (BOR) will be derived based on the CR secondary endpoint rules by Novartis as below:

- CR = at least one determination of CR without progression or relapse from CR within the four after CR.
- mCR = at least one determination of mCR (and not qualifying for a CR).
- PR = at least one determination of PR (and not qualifying for a CR/mCR).
- SD = at least one SD assessment and not qualifying for CR, mCR or PR.
- PD = progression after enrollment and not qualifying for CR, mCR, PR or SD.
- UNK = all other cases (i.e., not qualifying for confirmed CR or mCR or PR and without SD or progression).

Details on the definition of response categories which are to be captured in the eCRF by the investigator were defined in Table 8-2 of the protocol that was copied into Table 2-6 below.

Table 2-6 Modified response classification per IWG criteria in MDS

| Response category | Definition [#] |
|-------------------|-------------------------|
|-------------------|-------------------------|

| | |
|--|--|
| Complete remission (CR) | 
Bone marrow: $\leq 5\%$ blasts with normal maturation of all cell lineages. (Note: Persistence of dysplasia will be noted but does not preclude achievement of complete remission [CR])
 
Peripheral blood
 
 1. Hgb ≥ 10 g/dL AND 2. Platelets $\geq 100*10^9/L$ AND 3. Neutrophils $\geq 1.0*10^9/L$ AND 4. Blasts 0% 
Note: the subject must not receive RBC or platelet transfusions, myeloid growth factor within 2 weeks before this disease assessment
 |
| marrow Complete remission (mCR) | 
Bone marrow: $\leq 5\%$ blasts and blast count decrease by $\geq 50\%$ compared to baseline
 
Peripheral blood/transfusion: Marrow CR may be achieved with or without improved blood counts or with or without transfusions
 |
| Partial remission (PR) | 
All CR criteria except
 
Bone marrow: $\geq 50\%$ decrease from baseline in blasts in bone marrow AND blast count in bone marrow $>5\%$
 |
| Stable Disease (SD) | Failure to achieve at least PR, but no evidence of progression for >8 weeks |
| Relapse from CR | 
Only in subjects with a CR:
 
At least 1 of the following criteria is met:
 
[In absence of another explanation not due to MDS, such as acute infection, bleeding, hemolysis, etc. Note that observation of peripheral blasts is not a sufficient criterion for relapse. However in that case, a bone marrow examination should be made to determine whether relapse has occurred.]
 
 • Return to baseline bone marrow blast percentage • Decrease of $\geq 50\%$ from maximum remission/response*** levels in neutrophils AND neutrophils $<1.0*10^9/L$. Note: neutrophils counts during periods of active infection will not be considered in determining the maximum • Decrease of $\geq 50\%$ from maximum remission/response*** levels in platelets AND platelets $<100*10^9/L$ • Decrease from maximum remission/response*** levels in Hgb concentration by ≥ 1.5 g/dL AND Hgb <10 g/dL • Becoming transfusion dependent** |

| | |
|----------------------------|---|
| Disease progression | 
At least 1 of the following criteria is met:
 
[In absence of another explanation not due to MDS, such as acute infection, bleeding, hemolysis, etc. Note that observation of peripheral blasts is not a sufficient criterion for progression. However in that case, a bone marrow examination should be made to determine whether relapse has occurred.]
 
Bone marrow according to the number of blasts of the subject at baseline:
 
 1. Less than 5% blasts at baseline: $\geq 50\%$ increase in blasts over baseline to $>5\%$ blasts 2. 5%- $<10\%$ blasts at baseline: $\geq 50\%$ increase over baseline to $>10\%$ blasts 3. 10%- $<20\%$ blasts at baseline: $\geq 50\%$ increase over baseline to $>20\%$ blasts. Subjects with more than 20% of blasts will be considered to have transformation to acute leukemia per 2016 WHO classification (Arber et al 2016) 
Peripheral blood:
 
 1. Decrease of $\geq 50\%$ from maximum remission/response*** levels in neutrophils AND neutrophils $<1.0 \times 10^9/L$. Note: neutrophils counts during periods of active infection will not be considered in determining the maximum 2. Decrease of $\geq 50\%$ from maximum remission/response*** levels in platelets AND platelets $<100 \times 10^9/L$ 3. Reduction from maximum remission/response*** levels in Hgb by $\geq 2\text{g/dL}$ AND Hgb $<10\text{g/dL}$ 
Becoming transfusion dependent** Occurrence of acute leukemia or extramedullary leukemia per investigator's judgement
 |
|----------------------------|---|

| Modified Hematological Improvement per IWG-MDS criteria in MDS (Cheson et al 2006) | |
|---|---|
| HI category | Definition[#] (HI must last at least 8 weeks) |
| Erythroid response (HI-E) (pretreatment*, $<11\text{ g/dL}$) | 
 1. Hgb increase from baseline by $\geq 1.5\text{ g/dL}$, in at least 2 consecutive Hgb measurements and maintained over at least 8 weeks 2. Relevant reduction from baseline of units of RBC transfusions by an absolute number of at least 4 RBC transfusions/8 weeks compared with the pre-treatment transfusion number in the previous 8 weeks. Only RBC transfusions given for a Hgb of $<9\text{ g/dL}$ pre-treatment will count in the RBC transfusion response evaluation. |
| Platelet response (HI-P) (pretreatment*, $<100 \times 10^9/L$) | 
 1. Absolute increase from baseline of $\geq 30 \times 10^9/L$ for subjects starting with $>20 \times 10^9/L$ platelets 2. Increase from baseline from $<20 \times 10^9/L$ to $>20 \times 10^9/L$ and by at least 100% for subjects starting with $<20 \times 10^9/L$ platelets |
| Neutrophil response (HI-N) (pretreatment*, $<1.0 \times 10^9/L$) | At least 100% increase and an absolute increase from baseline of $>0.5 \times 10^9/L$ |

#If not defined otherwise, all of the criteria apply. Words that are written in *italics* highlights the modifications from the IWG criteria described in the reference publications.

**Pretreatment counts correspond to the baseline (not influenced by transfusions)*

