**Table 2-1 Objectives and related endpoints**

Objective(s)	Endpoint(s)
Primary Objective 
 
To assess the safety profile of MBG453 (sabatolimab) 800 mg (every 4 weeks) given in combination with HMAs (IV/SC/Oral) by 12 months
 
	Endpoint for primary objective 
 
Incidence and severity of AEs and SAEs, changes in laboratory values and vital signs
 

Secondary Objectives 
 
To evaluate complete remission with MBG453 (sabatolimab) in combination with HMAs (IV/SC/Oral) in participants with intermediate, high, or very high risk MDS by 12 months
 
To evaluate PFS rate by 12 months with MBG453 (sabatolimab) combined with HMAs (IV/SC/Oral) in participants with intermediate, high or very high risk MDS
 
To assess Overall Survival rate by 24 months
 
To assess Leukemia-free survival rate by 12 months
 
To assess other response rates
 
To assess duration of complete remission
 
To assess time to complete remission
 
To assess the improvement in RBC/platelets transfusion independence
 
	Endpoints for other secondary objectives 
 
Complete remission (CR) rate according to International Working Group (IWG) for MDS (2006) * as per investigator assessment by 12 months.
 
PFS is defined as time from enrollment to disease progression (including transformation to leukemia per WHO 2016 classification), relapse from CR according to IWG-MDS * or death due to any cause, whichever occurs first, as per investigator assessment ** by 12 months post LPFT.
 
Overall survival, time from enrollment to death due to any cause during 12 months post LPFT.
 
Time from enrollment to <math>\geq 20\%</math> blasts in bone marrow/peripheral blood (per WHO 2016 classification) or death due to any cause
 
Percentage of CR/mCR/PR according to IWG-MDS as per investigator assessment
 

Objective(s)	Endpoint(s)
	

6) Time from the date of the first documented CR to the date of first documented relapse from CR or death due to any cause, whichever occurs first

7) Time from enrollment to the first documented CR

8) Number and percent of participants who are RBC/platelets transfusion independent after enrollment as per IWG-MDS

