Due to its correlation with overall survival, the emerging goal for HR-MDS is to achieve complete remission (the bone marrow and blood cell counts return to normal). Only 40% to 50% of patients typically will respond to HMAs, with a median duration of response < 1.5 years and eventually all patients will lose initial response. Outcome after HMA treatment failure is poor and represents an unmet need. Complete remission (CR) have shown to be associated with prolonged overall survival in MDS patients ([Komrokji 2015](#)).

In Komrokji 2015 study AZA001, for patients who were treated with HMA as first line therapy, the best response rates by IWG 2006 criteria were CR in 15%.

In Garcia-Manero ASH 2019, CR rate for HR MDS/CMML study the oral decitabine data shows CR as 12%.

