**Table 8-2 Modified response classification per IWG criteria in MDS**

([Platzbecker et al 2018](#), [Cheson et al 2006](#), [Cheson et al 2000](#))

Response category	Definition #
Complete remission (CR)	
Bone marrow:  <math>\leq 5\%</math> blasts with normal maturation of all cell lineages.            (Note: Persistence of dysplasia will be noted but does not preclude achievement of complete remission [CR])
 
Peripheral blood
 
 
1. Hgb <math>\geq 10</math> g/dL AND
 
2. Platelets <math>\geq 100*10^9/L</math> AND
 
3. Neutrophils <math>\geq 1.0*10^9/L</math> AND
 
4. Blasts 0%
 
 
Note: the participant must not receive RBC or platelet transfusions, myeloid growth factor within 2 weeks before this disease assessment

marrow Complete remission (mCR)	
Bone marrow:  <math>\leq 5\%</math> blasts and blast count decrease by <math>\geq 50\%</math> compared to baseline
 
Peripheral blood/transfusion:            Marrow CR may be achieved with or without improved blood counts or with or without transfusions

Partial remission (PR)	All CR criteria except Bone marrow: $\geq 50\%$ decrease from baseline in blasts in bone marrow AND blast count in bone marrow $>5\%$
Stable Disease (SD)	Failure to achieve at least PR, but no evidence of progression for $>8$ weeks

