2.10 Interim analysis

An interim analysis was performed after all subjects who have completed 6 months follow-up from enrollment (cycle 1 day 1) or discontinued earlier for publication purpose.

Final Analysis will be performed when all subjects complete the core and extension phase and safety follow-up or discontinued early. A final CSR will be written.

3 Sample size calculation

This is an open label, non-randomized, single-arm combination study to assess safety and efficacy of MBG453 (sabatolimab) given with HMAs of investigator's choice (IV/ SC/ Oral). The primary objective of the study is to assess safety profile of this combination drug by 12 months.

Given the above expected incidence rates of AEs with the combination (Table 1-3 of protocol), a sample size of 81 evaluable subjects is estimated based on a two sided 95% confidence interval for an incidence rate of an AE using the large sample normal approximation that will extend 0.10 from the observed incidence rate of an AE (precision or margin of error of 10%) for an expected incidence rate of 30%.

Thus, with the estimated sample size of 90 subjects there is at least 90% probability to detect an AE with a true incidence rate of 2.5%. Considering drop-out rate of 10%, approximately 90 subjects will be enrolled for safety and efficacy assessment of this study.

Novartis has decided to permanently halt recruitment based on a re-evaluation of the development strategy for sabatolimab. Subjects who are currently on study treatment or in follow-up will be continue per the protocol. At the time of this amendment, 39 subjects have been enrolled into the study.

4 Change to protocol specified analyses

- [REDACTED]
- [REDACTED]
- No supportive/subgroup/sensitivity analysis performed due to MBG program closing/due to fewer sample size. Additionally it is mentioned in protocol that subgroup analysis may be performed. Hence it is agreed to not have these analysis.

5 Appendix

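### CR is named as IWG 2006 but derived only with modified IWG criteria, and the analysis that would show the difference is dropped

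*SAP*

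**What the plan says.** **The name.** Protocol Table 2-1 lists the endpoint as "Complete remission (CR) rate according to International Working Group (IWG) for MDS (2006", assessed by the investigator by 12 months. Protocol 12.5.1.1 and SAP Table 1-1 use the same 2006 label, and SAP 2.7.1.1 repeats it: "Complete remission rate will be assessed according to International Working Group (IWG) for MDS (2006".

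**The criteria applied.** Protocol 8.3 sends the reader to Table 8-2, titled "Modified response classification per IWG criteria in MDS", which cites three IWG publications and not only the 2006 one. The SAP copies it as Table 2-6. The response assessment rules in SAP 2.7.1.1 have investigators score responses "using the modified version of the published response criteria IWG for MDS", and best overall response is derived from those scores. The legend to Table 2-6 says that italic type "highlights the modifications from the IWG criteria described in the reference publications".

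**The bridging analysis.** SAP 2.7.1.1 states: "A sensitivity analysis may be performed for CR by considering IWG-MDS & modified IWG-MDS of Peripheral blood". SAP section 4, on changes to the protocol-specified analyses, then states: "No supportive/subgroup/sensitivity analysis performed due to MBG program closing/due to fewer sample size".

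**The benchmark.** Protocol 4.1, discussing first-line HMA treatment, says that "the best response rates by IWG 2006 criteria were CR in 15" per cent.

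**The concern.** The label and the derivation point to different definitions. A reader of the results would see a CR rate under the IWG 2006 name and reasonably take it as such. It would in fact be a modified-criteria rate, and the rate named in the objectives would appear nowhere.

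This matters because the study has one arm. CR can be interpreted only against outside rates, and protocol 4.5 already reasons this way when it sets early combination results beside historical data. If the definitions classify even a few participants differently, part of any gap from the benchmark comes from the definition and not from the treatment. A confidence interval does not show that part.

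**Working it through.** **1. Is there a planned figure to reproduce?** Not for CR. The only sample-size figure concerns adverse-event precision: 1.96² × 0.30 × 0.70 / 0.10² = 80.67, rounded up to 81, which matches the protocol. It has no bearing on CR.

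**2. Name against derivation.**

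| Place | What it calls the criteria |
|---|---|
| Protocol Table 2-1 and 12.5.1.1; SAP Table 1-1; SAP 2.7.1.1 opening | IWG 2006 |
| Protocol Table 8-2; SAP Table 2-6; SAP response assessment rules | modified IWG |
| SAP 2.7.1.2 (relapse from CR, as a PFS event) | modified IWG |

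The third row shows that the accurate label is already used in the SAP for PFS. It is missing for CR.

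**3. Does the modification reach CR itself?** Yes, on the SAP's own wording: the optional analysis contrasts two versions of the peripheral-blood criteria specifically for CR. Which item changed is less clear. The modifications are marked only by italics. In the text as extracted from PDF, italics survive in the CR row only on the two-week exclusion of transfusions and growth factor before the assessment. Italics may have been lost elsewhere, and neither document prints the unmodified criteria.

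**4. Is any other CR derivation left?** No. The only analysis using both versions was optional, and SAP section 4 drops it with all other sensitivity analyses. The supporting remark there, that the protocol makes such work optional, refers to subgroup analyses. For a different set of CR sensitivity analyses (excluding discontinued, transplanted and progressed participants), protocol 12.5.1.1 and SAP 2.7.1.1 both still say they are to be done where appropriate. Section 4 conflicts with that text too.

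**5. Scale.** Inputs: 39 enrolled (SAP 1.1), all assumed to be in the FAS; exact 95% CI (SAP 2.7.1.1); benchmark 15% (protocol 4.1).

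- One reclassified participant: 1/39 = 2.6 points.
- The 15% benchmark in this sample: 0.15 × 39 = 5.85, about 6 participants.

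As an illustration only, assume 6 of 39 are CR under the modified criteria, and that 0 to 3 of them are not CR under the unmodified criteria:

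| CR count | Rate | Exact 95% CI |
|---|---|---|
| 6/39 | 15.4% | 5.9 to 30.5% |
| 5/39 | 12.8% | 4.3 to 27.4% |
| 4/39 | 10.3% | 2.9 to 24.2% |
| 3/39 | 7.7% | 1.6 to 20.9% |

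The starting count, the number reclassified and the downward direction are all assumptions. An upward shift has the same step size.

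**6. Can the named endpoint still be computed?** Yes, in principle. The SAP lists laboratory values by subject and visit (2.8.3), response assessments and marrow blast percentages (2.7.1), and transfusions and concomitant medications (2.4.2).

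**The case against.** The best case for the plan is that this is shorthand. The tables are titled as modified, the response rules and the PFS section say so, and the operational CR definition is printed in full, so a careful reader can see what was counted. The bridging analysis was only optional, and the SAP openly records that it was dropped. CR is a secondary, descriptive endpoint with no hypothesis test, and with 39 participants the sampling error is large: at 6/39 the interval runs from 5.9 to 30.5%.

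Much of that stands, and it rules out several stronger readings that a reader might infer:

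- *CR cannot be compared with published rates.* Too strong. The data for a re-derivation are collected and listed.
- *The comparison is biased in a known direction or by a known amount.* Unsupported. The unmodified criteria are not in the documents. The one modification still visible, an added exclusion, would by itself make CR harder to reach, and it may not be the only change.
- *All the cited CR rates are IWG 2006 rates.* Only the 15% is described that way. The 9% and 17% in protocol 1.1 and the 12% in protocol 4.1 carry no criteria version, so they cannot be used to size a criteria mismatch.
- *The modification is hidden.* It is disclosed in the table titles. The endpoint name simply does not carry it.

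What the objection does not answer is that the endpoint as named is never computed. A wide interval expresses sampling error and does not tell the reader that the definition differs. Nor does a small sample prevent reporting one more descriptive proportion.

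**Conclusion.** The point holds as a mismatch between label and derivation, with a consequence for interpretation. If the plan is followed, a modified-criteria CR rate is reported under the IWG 2006 name, and the difference is left unquantified. The rate is not like-for-like with the 15% benchmark.

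The size and direction are unknown from the documents. All that can be stated is the step of 2.6 points per reclassified participant, on a denominator of 39. The conclusion rests on the SAP's own distinction between the two versions of the blood criteria for CR, and on reading SAP section 4 as cancelling the comparison of them. It does not depend on any particular threshold having changed.

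**What to change.** 1. Name the reported endpoint *CR by modified IWG criteria*, in line with the wording SAP 2.7.1.2 already uses for relapse, and list in words which items were modified, since italics alone do not carry the information reliably.
2. Add one descriptive row: CR under the full unmodified IWG 2006 peripheral-blood criteria (every item, not only the count thresholds), with an exact 95% CI. The current SAP addendum is itself dated after database lock, so mark the row as a post-lock addition.
3. Reconcile SAP section 4 with SAP 2.7.1.1, saying for each CR sensitivity analysis whether it is done or dropped, and why.
4. If the row is not added, at least relabel the endpoint and footnote the difference wherever the result is set beside the 15%.

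The cost is a label change, one table row and limited programming on data already collected. If the unmodified criteria prove less strict, moving someone up to CR also needs the marrow maturation finding, which may mean consulting the pathology reports collected under protocol 8.3. The downside is a second CR figure that may differ from the first.
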